12.3 Statistical Analysis

Detailed statistical analysis will be described in the Statistical Analysis Plan (SAP). The plan will be finalised before breaking the blind.

12.3.1 Descriptive statistics

Descriptive statistics for PK variables (except for t_{\max}) will include n (number of observed values), arithmetic mean, standard deviation (SD), coefficient of variation (CV), geometric mean, geometric CV, median, minimum, and maximum. The variable t_{\max} will be summarised by using n, median, minimum, and maximum.

All individual concentration data and PK variables will be listed. In addition, a listing of the actual sampling times relative to study treatment administration will be provided. Concentrations will be summarised by treatment and scheduled sampling time by using n, arithmetic mean, SD, CV, median, minimum, and maximum.

Descriptive statistics for the other continuous variables will include n, arithmetic mean, SD, median, minimum, and maximum.

For categorical variables, the number and percentage of subjects with a specific level of the variable will be presented. Missing values will not be used in percentage calculations.

12.3.2 Missing data

Further details on dealing with missing data, along with the handling of possible outliers, will be described in the SAP. Other critical missing data, if any, will be discussed during the review of the data. Decisions will be fully documented in the Data Review Report.

Clinical Study Code No.: CLI-10067AA1-01	Version No.: 6.0
EUDRACT No.: 2022-001079-15	Date: 06 July 2023

12.3.3 Subject demographics and baseline characteristics

The following variables will be summarised using descriptive statistics on the safety population (and on the PK population, if relevant): demographic characteristics (including age, sex, and race), height, weight, BMI, medical history and concomitant diseases, previous and concomitant medications, lung function, diffusing capacity, oxygen saturation, 12-lead ECG, vital signs, laboratories, and other safety parameters at screening and/or at baseline (pre-dose on Day 1).

12.3.4 Pharmacokinetic variables

CHF10067 serum AUC_{0-t} , AUC_{inf} , C_{max} , t_{max} , C_{inf} , CL, Vz, and $t_{1/2}$ will be summarised by dose level using descriptive statistics.

Serum concentration/time curves will be presented in linear/linear and log/linear scale. Plots will be presented by dose level, based on arithmetic means, and by subject, by showing the individual curves grouped by dose level (1 plot for each dose level) and ADA positivity/negativity (using different colours).

Dose proportionality in terms of CHF10067 AUC_{0-t} , AUC_{inf} , and C_{max} will be evaluated using the power model, including the log-transformed PK parameters as dependent variables, and the log-transformed CHF10067 dose as a covariate. The slope for log-transformed dose will be estimated with its 90% confidence interval (CI) to examine dose proportionality.

12.3.5 Safety variables

All safety data will be listed. For all safety and immunogenicity variables, baseline is the last available assessment before the dose administration, which is either the screening assessment between Days -28 to -3 or the pre-dose assessment on Day 1.

12.3.5.1 Adverse events

The number of events and the number and percentage of subjects experiencing treatment emergent-adverse events (TEAEs), treatment-emergent ADRs, serious TEAEs, non-serious TEAEs, TEAEs by CTCAE grade, TEAEs leading to discontinuation of study drug and TEAEs leading to death will be presented by treatment. The aforementioned categories of AEs will be also summarised by System Organ Class and Preferred Term using the MedDRA dictionary.

12.3.5.2 Systemic markers for evaluation of immediate hypersensitivity reactions

Cytokine markers (IFN- γ , TNF- α , IL-1 β , IL-2, IL-4, IL-6, IL-8, IL-10, IL-12 (p70), and IL-13), mast cell tryptase, complement markers (C3a, C5a, CH50, and SC5b-9), and CHF10067 IgE will be presented by subject for each post-dose timepoint as absolute value and change from baseline (if collected).

Clinical Study Code No.: CLI-10067AA1-01	Version No.: 6.0
EUDRACT No.: 2022-001079-15	Date: 06 July 2023

12.3.5.3 Immunogenicity

Anti-drug antibody positive subjects will be defined as described in [Section 7.2.2.4](#).

As a minimum, the following will be prepared:

- A table summarising for each ADA-positive subject:
 - dose administered
 - baseline ADA
 - maximal ADA timepoint
 - maximal ADA value
 - final ADA timepoint
 - final ADA value
 - pre-dose TG2 level
 - TG2 level at maximal ADA timepoint
 - CHF10067 AUC_{inf}.
- A table summarising for ADA-positive subject the ADA and nAb ranges by dose level.

12.3.5.4 Pulmonary assessments

12.3.5.4.1 Spirometry

The FEV₁, FVC, FEV₁/FVC, FEV₁% of predicted and FVC% of predicted, will be summarised by dose level as absolute value, and absolute and relative change from baseline (i.e., the assessment at screening between Days -28 to -3) at each post-dose timepoint using descriptive statistics and 95% CIs. The frequency of subjects with FEV₁% and FVC% below the lower limit of normal at each timepoint will be listed and summarised with descriptive statistics.

Time profile plots by dose level will be presented for mean absolute and relative changes from baseline.

12.3.5.4.2 Diffusing capacity

The D_{LCO} unadjusted, D_{LCO} % predicted, D_{LCO} corrected for haemoglobin, and the other relevant variables collected will be summarised by dose level as absolute value and change from baseline (i.e., the assessment at screening between Days -28 to -3) at each post-dose timepoint using descriptive statistics and 95% CIs.

Time profile plots by dose level will be presented for D_{LCO} corrected for haemoglobin and D_{LCO}% predicted for mean changes from baseline.

12.3.5.4.3 Oxygen saturation

The oxygen saturation will be summarised by dose level as absolute value and change from baseline (i.e., the pre-dose assessment on Day 1) at each post-dose timepoint using descriptive

Clinical Study Code No.: CLI-10067AA1-01	Version No.: 6.0
EUDRACT No.: 2022-001079-15	Date: 06 July 2023

statistics and 95% CIs. Time profile plots by dose level will be presented for mean changes from baseline.

12.3.5.5 ECG

At each post-dose timepoint, the following statistics will be presented by dose level for 12-lead ECG parameters (heart rate, PR, QRS, QTcF):

- mean absolute value with its 95% CI
- mean change from baseline (i.e., the pre-dose assessment on Day 1) with its 90% CI
- mean placebo-corrected change from baseline with its 90% CI.

Time profile plots, individual and by dose level, will be presented for change from baseline (i.e., the pre-dose assessment on Day 1). Time profile plots of mean difference versus placebo in change from baseline will be presented by dose level for heart rate and QTcF.

The number and percentage of subjects with the following will be presented by dose level at each post-dose timepoint and at any post-dose timepoint:

- Males: QTcF > 450 ms, > 480 ms, and > 500 ms
- Females: QTcF > 470 ms and > 500 ms
- Both sexes: change from baseline in QTcF > 30 ms and > 60 ms.

12.3.5.6 Vital signs

At each post-dose timepoint the following statistics will be presented by dose level for systolic and diastolic blood pressure, pulse rate, respiratory rate, and body temperature:

- mean absolute value with its 95% CI
- mean change from baseline (i.e., the pre-dose assessment on Day 1) with its 95% CI.

Time profile plots, individual and by dose level, will be presented for change from baseline (i.e., the pre-dose assessment on Day 1).

In addition, the number and percentage of subjects with a change from baseline > 20 mmHg for systolic blood pressure and > 10 mmHg for diastolic blood pressure will be presented by treatment at each post-dose timepoint and at any post-dose timepoint.

12.3.5.7 Safety laboratory data

At each post-dose timepoint quantitative laboratory parameters will be summarised by treatment as absolute value and change from baseline using descriptive statistics and 95% CIs.

Shift tables from baseline to the minimum and the maximum post-dose value, with regards to normal range, will be presented by treatment.

Clinical Study Code No.: CLI-10067AA1-01	Version No.: 6.0
EUDRACT No.: 2022-001079-15	Date: 06 July 2023

Urinalysis parameters will be presented in the listings.

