10.3 Intensity of Adverse Event

For the classification of AEs severity (except for immediate hypersensitivity reactions severity, see below), the Common Terminology Criteria for Adverse Events (CTCAE) [23] will be used:

- Grade 1 Mild; asymptomatic or mild symptoms; clinical or diagnostic observations only; intervention not indicated.
- Grade 2 Moderate; minimal, local, or noninvasive intervention indicated; limiting age-appropriate instrumental Activities of Daily Living (ADL)*.
- Grade 3 Severe or medically significant but not immediately life-threatening; hospitalization or prolongation of hospitalization indicated; disabling; limiting self-care Activities of Daily Living**.
- Grade 4 Life-threatening consequences; urgent intervention indicated.
- Grade 5 Death related to AE.

*Instrumental ADL refer to preparing meals, shopping for groceries or clothes, using the telephone, managing money, etc.

**Self-care ADL refer to bathing, dressing and undressing, feeding self, using the toilet, taking medications, and not bedridden.

In order to guarantee objectivity and consistency in the evaluation of AEs (including classification of severity), the proposed guidance should be followed in alignment with best medical practice.

Laboratory abnormalities and other clinical assessments (e.g., 12-lead ECG) will be reported as AEs if judged by the Investigator as being clinically significant.

In case of laboratory evaluations or other clinical assessments (e.g., 12 -lead ECG) not listed in the CTCAE grading table, the AE severity will be judged by the Investigator based on the local ranges.

Taking into consideration the disease examined in the current study, it should be acknowledged that the guidance may not always be applied. Therefore, although the guidance should be followed, whenever possible, in order to ensure an accurate and objective evaluation of the AEs, the final decision on the severity classification remains the responsibility of the Investigator.

For the specific classification of severity and management of immediate hypersensitivity reactions, refer to [Section 7.2.2.5.1](#).

Clinical Study Code No.: CLI-10067AA1-01	Version No.: 6.0
EUDRACT No.: 2022-001079-15	Date: 06 July 2023

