bias	The systematic tendency of any factors associated with the design, conduct, analysis and evaluation of the results of a clinical trial to make the estimate of a treatment effect deviate from its true value. Bias introduced through deviations in conduct is referred to as 'operational' bias. The other sources of bias listed above are referred to as 'statistical'.
case report form (CRF)	A printed, optical, or electronic document designed to record protocol required information to be reported to the sponsor for each trial subject.
display	Analysis table, listing or figure
missing data	Data that would be meaningful for the analysis of a given endpoint but were not collected. They should be distinguished from data that do not exist.
phase	Interval of time in the planned conduct of a study associated with a specific purpose: for example, screening, treatment, follow-up.
significant digit	All digits of a number used to express it to the required degree of accuracy, starting from the first non-zero digit.
standardised unit	unit populating --STRESU in the clinical database
treatment-emergent abnormality	Any postbaseline abnormality/toxicity that was not present at baseline (e.g., glucose low at baseline and high post-baseline; QTcF]450; 480] ms at baseline and >500 ms post-baseline)

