3.2.2 Derivation rules

Since not all the clinical sites involved in the study are able to provide WBC differential results but rather WBC absolute count results only, the WBC differential values at the given timepoint/assessment will be derived according to the following formula:

$$WBC \text{ type differential } (\%) = \left(\frac{WBC \text{ type } (count)}{WBC \text{ total } (count)} \right) * 100$$

where WBC types are: neutrophils, eosinophils, lymphocytes, monocytes and basophils.

Derived differential values will be used for analysis purposes, while observed differential values (when available) will be listed only.

The following abnormality categories will be defined:

- Low: value < lower limit of normal range;
- Normal: lower limit of normal range \leq value \leq upper limit of normal range;
- High: value > upper limit of normal range.

Notes:

- No normal ranges will be available for the derived WBC type differentials.

- Classification will be done in standardised units, by using non-imputed values and limits as reported in standardized units in the clinical database: a value $<X$ where X equals the lower limit of normal range will be classified as low. A value X with normal range $<X$ will be classified as high.
- If not straightforward how to categorize results, e.g. when results are reported as ranges, a worst-case approach will be used. A value of '4 to 6' with normal range '0 to 5' will thus be classified as normal for pre-dose assessments but as high for post-dose assessments.

3.2.3 *Presentation of results*

The statistical analysis will present results in standardised units.

Continuous laboratory parameters (biochemistry and haematology) will be summarised by means of descriptive statistics at each analysis visit by treatment. Actual values and changes from baseline will be tabulated. Categorical parameters will be listed only.

Laboratory abnormalities will be presented by treatment as cross-tabulations of the abnormality at each post-dose analysis visit and at the worst-case analysis visit versus the baseline abnormality.

All laboratory data will be listed.

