14.3.1.6	Serious ADRs by System Organ Class and Preferred Term (Safety Set) Tabulation of the number and percentage of subjects with serious ADRs by MedDRA system organ class and preferred term. The number of events will also be shown.	SAF	AET003
14.3.1.7	Grade 3 or 4 TEAEs by System Organ Class and Preferred Term (Safety Set) Tabulation of the number and percentage of subjects with grade 3 or 4 TEAEs by MedDRA system organ class and preferred term. The number of events will also be shown.	SAF	AET003
14.3.1.8	TEAEs Leading to Study Treatment Discontinuation by System Organ Class and Preferred Term (Safety Set) Tabulation of the number and percentage of subjects with TEAEs leading to study treatment discontinuation by MedDRA system organ class and preferred term. The number of events will also be shown.	SAF	AET003
14.3.1.9	TEAEs Leading to Death by System Organ Class and Preferred Term (Safety Set) Tabulation of the number and percentage of subjects with TEAEs leading to death by MedDRA system organ class and preferred term. The number of events will also be shown.	SAF	AET003
LABORATORY DATA			
14.3.2.1	Haematology: Summary of Actual Values and Changes from Baseline (Safety Set) Descriptive statistics of haematology results and changes from baseline by treatment, parameter and analysis visit. Table sorted first by parameter, then by analysis visit. Each parameter will begin on a new page.	SAF	LBT001
14.3.2.2	Haematology: Shift from Baseline (Safety Set) [KFR] Shift table of the abnormality at each analysis visit versus the baseline abnormality per parameter. Each parameter will begin on a new page.	SAF	LBT005

	Statistical Analysis Plan		
CLI-10067AA1-01	Final Analysis	Final 1.0	of 30MAY2024

Number	Title	Analysis Set	TLFs Library Template Number
14.3.2.3	Biochemistry: Summary of Actual Values and Changes from Baseline (Safety Set) Descriptive statistics of biochemistry results and changes from baseline by treatment, parameter and analysis visit. Table sorted first by parameter, then by analysis visit. Each parameter will begin on a new page.	SAF	LBT001
14.3.2.4	Biochemistry: Shift from Baseline (Safety Set) [KFR] Shift table of the abnormality at each analysis visit versus the baseline abnormality per parameter. Each parameter will begin on a new page.	SAF	LBT005
VITAL SIGNS			

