16.2.7.9	Treatment Emergent Adverse Events Leading to Death (Randomised Set) Same as listing 16.2.7.2, but listing TEAEs leading to death only	RND	AEL002
16.2.7.10	Immediate Hypersensitivity Reactions (Randomised Set) Listing IHR along with associated signs/symptoms and suspected anaphylaxis and a reference to the related adverse event(s).	RND	AEL002
16.2.7.11	Physical Examination Abnormalities (Randomised Set) Listing of all data on abnormal physical examinations findings	RND	PEL001
LABORATORY DATA			
16.2.8.1	Laboratory Results: Haematology Full Listing (Randomised Set) Listing of all haematology results. The (non-imputed) values will be shown, as well as normal ranges, abnormality flags (L/H), clinical significance flag and fasted flag. Treatment-emergent abnormalities will be flagged.	RND	LBL001
16.2.8.2	Laboratory Results: Haematology Abnormalities (Randomised Set) Same as listing 16.2.8.1, but listing abnormal results only	RND	LBL001
16.2.8.3	Laboratory Results: Biochemistry Full Listing (Randomised Set) Same as listing 16.2.8.1, but listing biochemistry results instead	RND	LBL001
16.2.8.4	Laboratory Results: Biochemistry Abnormalities (Randomised Set) Same as listing 16.2.8.3, but listing abnormal results only	RND	LBL001
16.2.8.5	Laboratory Results: Urinalysis (Randomised Set) Listing of all urinalysis results. The (non-imputed) values will be shown, as well as normal ranges, abnormality flags (L/H/A), and clinical significance flag.	RND	LBL001
16.2.8.6	Laboratory Results: Pregnancy Test (Randomised Set) Listing of all serum and urine pregnancy results.	RND	LBL005
VITAL SIGNS			
16.2.9.1	Vital Signs: Full Listing (Randomised Set) Listing of all vital signs results, including oxygen saturation. The values will be shown, as well as changes from baseline and change abnormalities. Treatment-emergent abnormalities will be flagged.	RND	VSL002

	Statistical Analysis Plan		
CLI-10067AA1-01	Final Analysis	Final 1.0	of 30MAY2024

Number	Title	Analysis Set	TLFs Library Template Number
ECG			
16.2.10.1	Local 12-Lead ECG: Full Listing (Randomised Set)	RND	EGL001
	Listing of all triplicate/single local 12-lead ECG results and the corresponding interpretation. The values will be shown, as well as changes from baseline and abnormality categories (for QTcF). Treatment-emergent abnormalities will be flagged.		
16.2.10.2	Local 12-Lead ECG: Abnormalities (Randomised Set)	RND	EGL001

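### Laboratory shift tables and treatment-emergent flags cannot register worsening in a test already out of range at baseline; a graded shift table by treatment would be a cheap improvement

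*Protocol*

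**What the plan says.** SAP 3.2.2 sets the laboratory classes. Apart from Normal there are two: "Low: value < lower limit of normal range" and "High: value > upper limit of normal range". Neither side has a second tier, a multiple of the limit, or a threshold for change from baseline.

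SAP 3.2.3 uses these classes: "Laboratory abnormalities will be presented by treatment as cross-tabulations of the abnormality at each post-dose analysis visit", and again at a worst-case visit, against the baseline class. The outputs are Tables 14.3.2.2 (haematology) and 14.3.2.4 (biochemistry), both marked as key first results. Each is described in SAP 9.1 as "Shift table of the abnormality at each analysis visit versus the baseline abnormality per parameter".

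The SAP's Definition of Terms describes a treatment-emergent abnormality as "Any postbaseline abnormality/toxicity that was not present at baseline". SAP 9.2 applies this to the haematology listing, 16.2.8.1: "Treatment-emergent abnormalities will be flagged". Listings 16.2.8.2 to 16.2.8.4 are built the same way.

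Protocol 12.3.5.7 fixes only the normal-range basis of the shift tables: "Shift tables from baseline to the minimum and the maximum post-dose value, with regards to normal range, will be presented by treatment". It asks for two shifts, one to the minimum and one to the maximum post-dose value.

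Protocol 10.3 adopts CTCAE (version 5.0 in the reference list) for grading adverse events. A laboratory value reaches that scale only through investigator judgement: "Laboratory abnormalities and other clinical assessments (e.g., 12-lead ECG) will be reported as AEs if judged by the Investigator as being clinically significant".

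**The concern.** Safety and tolerability are the primary objective, and each dose has six active subjects, so one marked laboratory change may be the whole signal. The key laboratory tables give a result just over the limit and one many times over it the same label. For a subject already above the limit at baseline, no further rise can change the cell or raise the flag. The same holds for a further fall in a value already below the lower limit.

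Such subjects can enter. Exclusion criterion 24 rests on the investigator's view of clinical relevance and sets no numeric limit. A reader of the shift tables could therefore see no movement in a test that had worsened sharply, and would find no count by treatment elsewhere to correct that impression.

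**Working it through.** The plan states no figure on this point, so there is none to reproduce. The check applies the SAP's own rules to test values.

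**1. Classification.** Values are expressed as multiples of ULN. The rule is High if the value exceeds 1. A result is treatment-emergent if its post-dose class is abnormal and differs from the baseline class.

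| Baseline (x ULN) | Post-dose (x ULN) | Tabulated as | Flagged |
|---|---|---|---|
| 0.9 | 1.05 | Normal to High | yes |
| 1.1, 1.5 or 2.0 | 1.05, 3, 5.5, 10 or 20 | High to High in all 3 x 5 = 15 pairings | no, in all 15 |

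**2. Comparison with other safety measures in the same SAP.**

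| Measure | Tiers on actual value | Thresholds for change |
|---|---|---|
| QTcF (3.4.2) | males above 450, 480, 500 ms; females above 470, 500 ms | increase above 30 and above 60 ms |
| Blood pressure (3.3.2) | none | above 20 mmHg systolic and above 10 mmHg diastolic, each direction |
| Laboratory (3.2.2) | one limit on each side | none |

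One example in the Definition of Terms is a QTcF between 450 and 480 ms at baseline that exceeds 500 ms after dosing. It counts worsening within an abnormal range as treatment-emergent. That can work only where tiers exist, and laboratory tests have none.

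**3. What the continuous summary shows.** Assume that one of six subjects rises from 1.5 to 10 x ULN, that the other five do not change, and that all share one ULN. The changes are 8.5, 0, 0, 0, 0, 0.

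- Mean = 8.5 / 6 = 1.42; SD = 3.47; median = 0.
- 95% CI = 1.42 ± t(0.975; 5 df) x 3.47 / √6 = -2.22 to 5.06.
- Maximum = 8.5.

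Only the maximum points clearly to the case. It says that someone rose, not how many did. In the real tables it is in standardised units, not relative to each laboratory's own limit.

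**4. How likely a subject is to start above the limit.** The documents give no prevalence, so it is assumed. With proportion p High at baseline for a given test, the chance of at least one such subject among the 18 active subjects (3 cohorts x 6) is 1 - (1 - p)^18.

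| p (assumed) | Chance of at least one |
|---|---|
| 5% | 60% |
| 10% | 85% |
| 20% | 98% |
| 30% | over 99% |

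This is the chance that someone sits where the tables cannot show worsening. It is not the chance that anyone worsens.

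**The case against.** A reader might infer that a marked toxicity would be hidden. The documents do not support that.

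- Listings 16.2.8.1 to 16.2.8.4 show each value with its normal range, a low or high flag and a clinical significance flag. Two of the four are restricted to abnormal results.
- The continuous tables give actual values and changes from baseline by visit and treatment, with minimum and maximum.
- Protocol 10.8 requires clinically significant changes after screening to be reported as adverse events. Protocol 10.3 grades them by CTCAE, and the SAP tabulates Grade 3 or 4 events. A large rise would escape that table only if the investigator judged it not clinically significant or graded it lower.

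Nor do the documents support a reading that dose escalation is compromised. Under Protocol 6.2.2.1, escalation rests on adverse event counts, the pattern of events, and a report of all available safety assessments for each subject. These shift tables belong to the final analysis, and no rule or threshold uses them.

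Two further arguments have weight. First, normal-range shifts are what the protocol prespecified, so their use is not an inconsistency. Second, exclusion criteria 11 and 24 and the requirement for well-tolerated, stable antifibrotic treatment may keep the number of subjects with abnormal baselines low.

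All of this stands, and it limits the point. It does not remove it. Listings give no count by treatment, the continuous tables do not say how many subjects worsened, and the adverse event route depends on a prior judgement. With this few subjects the listings can be read one by one, but that is an unplanned reading, not a prespecified summary.

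**Conclusion.** The point holds in a limited form. SAP 3.2.2 and the SAP's definition of treatment-emergent abnormality together mean that worsening in a test already out of range appears as no shift in Tables 14.3.2.2 and 14.3.2.4. It is also unflagged in Listings 16.2.8.1 to 16.2.8.4, while a trivial crossing of the limit is counted and flagged. This follows from the rules alone and rests on no assumption.

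Its practical size cannot be fixed from the documents. It depends on how many subjects enter with out-of-range values and how many of those worsen, and neither is given. The prevalences of 5% to 30% and the one-in-six example above are assumptions.

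What is lacking is a prespecified count, by treatment, of subjects whose laboratory results worsened. The information itself is kept. This is a cheap improvement to the reporting of the primary objective, not an error or a contradiction in the plan.

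**What to change.** In SAP 3.2.2 and 3.2.3:

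1. For each parameter with a numeric CTCAE v5.0 grade, derive that grade. For liver tests and creatinine, multiples of ULN would serve instead. State the cut-offs in the SAP, because the protocol gives only the general grade descriptions.
2. Add to Tables 14.3.2.2 and 14.3.2.4 a cross-tabulation by treatment of baseline grade against worst post-dose grade, separately for the low and high directions. This also matches the protocol's separate minimum and maximum shifts. The SAP has a single worst-case visit, gives it no direction for laboratory tests, and does not list the difference in section 7.1.
3. For graded parameters, flag any post-dose increase in grade over baseline as treatment-emergent.
4. Keep Low/Normal/High for the other parameters. The derived white cell differential percentages stay unclassified, since SAP 3.2.2 says they have no normal ranges.

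The cost is SAP wording and programming. Results and normal ranges are already collected (Protocol 7.2.2, SAP 3.2.1). The downsides are longer tables, and grades that rest on the numeric criterion alone where the full definition also needs clinical information.
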